### 12.3 Other safety endpoints

Tolerability assessment will be based on the evaluation of site administration adverse events.

## 13. DEVIATIONS FROM THE PROTOCOL SPECIFIED ANALYSIS

The worst skin toxicity during treatment and until 2 weeks after the last radiation will not be analyzed, as most of the patients reached G2 skin toxicity.

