7.3.5.2 Secondary endpoints

The median time to G2 radiation dermatitis development will be analyzed using Kaplan-Meier method. Comparisons between treatment groups will be performed using log-rank test.

The proportion of patients without G2 radiation dermatitis at week 6 for both cancer sites, at week 7 for head & neck cancer and 2 weeks after the last radiation for both cancer sites will be assessed and compared between treatment groups using chi-square test. Logistic regression will be used to obtain ORs, with 95% CIs, and to eventually adjust for covariates.

The worst skin toxicity during treatment and until 2 weeks after the last radiation will be compared between treatment groups using ANOVA.

The changes in skin erythema and pigmentation will be graphically described reporting the ITA (individual Typological Angle) degrees throughout the study. The ITA of the area treated with RT will be obtained averaging the ITA measured at the three different fixed regions, adjusted for the control measurement done in a specific contralateral area. Changes between visit 2, before the first RT session, and the end of RT and between the end of RT and the end of treatment will be analyzed and compared between treatment groups using ANCOVA, to adjust the estimates for baseline values.

The changes in trans-epidermal water loss (TEWL) will be graphically described reporting the Evaporation rate value (ERV, measured in g/m²h) throughout the study. The ERV of the area treated with RT will be obtained averaging the ERV measured at the five different fixed regions, adjusted for the control measurement done in a specific contralateral area. Changes between visit 2, before the first RT session, and the end of RT and between the end of RT and the end of treatment will be analyzed and compared between treatment groups using ANCOVA, to adjust the estimates for baseline values.

The mean and worst score of Skindex-16 questionnaire will be compared between treatment groups using ANCOVA, to adjust the estimates for baseline values.

Both the number of daily product applications reported on the patient's diary and the amount of used product, estimated through the difference in tubes weight between delivery to patient and return, will be used to assess the compliance to experimental treatment. The consistency between the two assessments will be checked through linear regression.

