#### **3.2 Secondary Objectives**

The secondary objectives of this clinical investigation are:

1. to evaluate the median time to G2 radiation dermatitis development according to CTCAE
2. to evaluate the proportion of patients without G2 radiation dermatitis at week 6 for both cancer sites, at week 7 for head & neck cancer and two weeks after the last radiation for both cancer sites .
3. to evaluate the worst skin toxicity during treatment and until 2 weeks after the last radiation, according to CTCAE
4. to evaluate changes in skin erythema and pigmentation and trans-epidermal water loss (TEWL)
5. to evaluate the mean and worst score of Patient Reported Outcome (PRO) with Skindex-16 questionnaire performed weekly
6. to evaluate the compliance to experimental treatment use
7. to evaluate the patient global satisfaction with treatment as assessed by Likert scale.

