#### **4.2 Treatment Administration**

Subjects have been randomly allocated to one of the following groups:

- Group A: Xonrid® gel + standard of care (SOC) preemptive treatment according to MASCC guidelines;
- Group B: standard of care (SOC) preemptive treatment according to MASCC guidelines.

Both Groups started treatment on the first day of radiotherapy and went on until two weeks after the last radiotherapy session.

Group B subjects received an additional standard treatment (according to Investigator's opinion) at G2 skin toxicity development.

All subjects interrupted the treatment and the study in the case of G3 skin toxicity development. This subjects have been treated according to the Investigator's opinion.

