#### 5.2 Secondary Endpoints

- Median time to G2 radiation dermatitis development according to CTCAE

- Proportion of patients without G2 radiation dermatitis at week 6 for both cancer sites, at week 7 for head & neck cancer and 2 weeks after the last radiation for both cancer sites.
- Worst skin toxicity during treatment and until 2 weeks after the last radiation, according to CTCAE
- Changes in skin erythema and pigmentation and trans-epidermal water loss (TEWL)
- Mean and worst score of Patient Reported Outcome (PRO) with Skindex-16 questionnaire performed weekly.
- Compliance to experimental treatment use
- Patient global satisfaction with treatment as assessed by Likert scale
- Study product safety and tolerability

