## 7. SAMPLE SIZE AND STATISTICAL POWER CONSIDERATION

In a previous observational study, 38.2% of the patients treated with SOC preemptive treatment according to MASCC guidelines did not reach G2 radiation dermatitis at week 5. In a pilot study using Xonrid®, the proportion of patients treated with Xonrid® and SOC preemptive treatment according to MASCC guidelines that did not reach G2 radiation dermatitis at week 5 was 82.9%.

According to these previous results, a two group chi-square test with a 0.05 two-sided significance level would have had 80% power to detect the difference between a proportion of patients that do not reach G2 of 38.2% in the Group B (standard of care (SOC) preemptive treatment according to MASCC guidelines) and a proportion of 82.9% in the Group A (Xonrid® and SOC preemptive treatment according to MASCC guidelines) when the sample size in each group is 18. To take into account a possible 10% dropout rate, 20 patients in each treatment group have been enrolled. As two cancer sites have been investigated, to assess the treatment effect within each site, 80 patients have been enrolled: 40 patients with breast cancer and 40 patients with head and neck cancer.

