## 9. GENERAL ISSUES FOR STATISTICAL ANALYSIS

### 9.1 Definitions, Derived Variables and Datasets

Analyses will be performed and report separately for each cancer site (i.e., breast cancer and head and neck cancer).

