### 14.2 Efficacy data

*Table 5.4.1.1.1. Number and proportion of subjects that reached and not reached G2 at week 5 (Breast cancer).*

*Table 5.4.1.2.1. Number and proportion of subjects that reached and not reached G2 at week 5 (Head and neck cancer).*

*Figure 5.4.2.1.1. Kaplan-Meier curves for time to G2 by treatment group (Breast cancer)*

*Table 5.4.2.1.1 Number and proportion of subjects that reached and not reached G2 at week 6 and 2 weeks after end of radiotherapy treatment (Breast cancer).*

*Table 5.4.2.1.2 Skindex-16 at Visits 7, 8, 9 and worst Skindex-16 observed in breast cancer patients*

*Table 5.4.2.1.3 Skindex-16 at Visits 7, 8, 9 and worst Skindex-16 Emotional observed in breast cancer patients*

*Table 5.4.2.1.4 Skindex-16 at Visits 7, 8, 9 and worst Skindex-16 Functional observed in breast cancer patients*

*Table 5.4.2.1.5. Changes in ITA among breast cancer patients*

*Figure 5.4.2.1.2 Mean ITA observed during the study (Breast cancer)*

*Table 5.4.2.1.6. Changes in TEWL among breast cancer patients*

*Figure 5.4.2.1.2. Mean TEWL observed during the study (Breast cancer)*

*Table 5.4.2.1.7. Patient's global satisfaction with treatment (Breast cancer)*

*Figure 5.4.2.2.1. Kaplan-Meier curves for time to G2 by treatment group (Head and neck cancer)*

*Table 5.4.2.2.1 Number and proportion of subjects that reached and not reached G2 at week 6 and 2 weeks after end of radiotherapy treatment (Head and neck cancer).*

*Table 5.4.2.2.2 Skindex-16 at Visits 7, 8, 9 and worst Skindex-16 observed in head and neck cancer patients*

*Table 5.4.2.2.3 Skindex-16 at Visits 7, 8, 9 and worst Skindex-16 Emotional observed in head and neck cancer patients*

*Table 5.4.2.2.4 Skindex-16 at Visits 7, 8, 9 and worst Skindex-16 Functional observed in head and neck cancer patients*

*Table 5.4.2.2.5. Changes in ITA among head and neck cancer patients*

*Figure 5.4.2.2.2 Mean ITA observed during the study (Head and neck cancer)*

*Table 5.4.2.2.6. Changes in TEWL among head and neck cancer patients*

*Figure 5.4.2.2.2. Mean TEWL observed during the study (Head and neck cancer)*

*Table 5.4.2.2.7. Patient's global satisfaction with treatment (Head and neck cancer)*

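### SAP section 13 drops the pre-specified analysis of worst CTCAE skin toxicity because of an observed outcome, and with it the only planned efficacy comparison that uses grades above the G2 cut

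*SAP*

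**What the plan says.** Protocol 5.2 lists worst CTCAE skin toxicity among the secondary objectives, and Protocol 7.3.5.2 gives it an analysis: "The worst skin toxicity during treatment and until 2 weeks after the last radiation will be compared between treatment groups using ANOVA".

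The SAP keeps the endpoint in two places. Section 3.2 has the objective "to evaluate the worst skin toxicity during treatment and until 2 weeks after the last radiation, according to CTCAE", and section 5.2 lists it again as an endpoint. Sections 11.4.2 and 11.5 contain no analysis of it, and section 14.2 contains no table. Section 13 explains why: it "will not be analyzed, as most of the patients reached G2 skin toxicity".

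On timing, SAP 1.1 lists one version, dated 18-Dec-2018. SAP 4.3 describes the study as open label, and SAP 7 states that "80 patients have been enrolled: 40 patients with breast cancer and 40 patients with head and neck cancer". On the unit of analysis, SAP 9.1 says: "Analyses will be performed and report separately for each cancer site".

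**The concern.** The reason given for the removal is a result of the trial, not a problem of feasibility or data quality. Dropping a pre-specified analysis because of an observed outcome creates a risk of selective reporting, and that risk is harder to dismiss in an open-label study.

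The reason also does not make the endpoint uninformative. Worst grade is an ordered scale. If nearly everyone reaches G2, a split at G2 carries little information, and the part of the scale where arms can still separate is G2 against G3 or higher. Under SAP 4.2 and Protocol 16.1, G3 is the grade that ends participation. Protocol section 3 also cites a lower G3 incidence with Xonrid in the pilot study than in the historical cohort. Without the worst-grade analysis, the planned efficacy results use no grade information above G2.

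**Working it through.** **1. What remains after the removal**

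| Planned analysis | Where | Use of grades above G2 |
|---|---|---|
| Proportion below G2 at week 5 | SAP 11.4.1 | None; G2 and G3 pooled |
| Proportion without G2 at week 6, at week 7 (head and neck), and 2 weeks after radiotherapy | SAP 11.4.2 | None; cut at G2 |
| Time to G2 | SAP 11.4.2 | None |
| ITA, TEWL, Skindex-16, compliance, satisfaction | SAP 11.4.2 | CTCAE grade not used |
| Dropout tables; discontinuation listing VI.1 | SAP 14; 16.1 | G3 withdrawals should appear; no test or estimate planned |
| Individual efficacy listing VI.6 | SAP 16.1 | Grades may be listed; no comparison |
| Severe AEs; withdrawals due to AE | SAP 12.2 | Safety comparison; G3 dermatitis may be only partly captured |

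The last row is limited by Protocol 14.3, which keeps signs of lack of efficacy out of the AE section unless they are serious or have another cause. No row gives an efficacy estimate that separates G3 from G2.

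**2. The plan's own sample size**

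Inputs from SAP 7: 38.2% vs 82.9% without G2 at week 5, two-sided 0.05, 80% power. The mean proportion is (0.382 + 0.829)/2 = 0.6055.

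n = [1.96·√(2 × 0.6055 × 0.3945) + 0.8416·√(0.382 × 0.618 + 0.829 × 0.171)]² / 0.447² = 17.5, so 18 per arm. With 10% dropout, 18/0.9 = 20. The stated figure reproduces, and 20 per arm within each cancer site is used below.

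**3. G3 rates in the documents**

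Protocol section 3 and SAP section 2 give G2 and G3 at week 5 as about 52% and 10% in the historical cohort and 15% and 2% in the pilot. These agree with the sample-size inputs: 100 − 52 − 10 = 38 and 100 − 15 − 2 = 83. Both sources are head and neck studies, so using them for breast is an assumption. The dropped endpoint runs to two weeks after the last radiation (about day 56 or 63). A patient's worst grade over that period cannot be below the grade at week 5, so the week-5 rates are a lower bound for worst grade. The documents give no full-course rates; the higher pairs below are assumptions.

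**4. Power of a G3-or-higher contrast, 20 per arm, two-sided 0.05**

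Power = Σₓ Σᵧ Bin(x; 20, p₁)·Bin(y; 20, p₂)·1[test rejects at (x, y)].

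| G3, SOC vs Xonrid | Expected patients | Chi-square | Fisher |
|---|---|---|---|
| 10% vs 2% (week 5, documents) | 2.0 vs 0.4 | 9% | 3% |
| 20% vs 4% (assumed) | 4.0 vs 0.8 | 34% | 20% |
| 30% vs 6% (assumed) | 6.0 vs 1.2 | 54% | 40% |
| 50% vs 10% (assumed) | 10.0 vs 2.0 | 84% | 74% |

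For precision at the low end, 2/20 vs 0/20 is a difference of 10 points, with a Newcombe 95% CI of −8 to 30.

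**5. Does a high G2 rate make worst grade uninformative?**

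Assume 90% in each arm reach G2 or higher, with G3 at 30% vs 6%. At 20 per arm, the chi-square on the G2 cut rejects about 4% of the time, which is no signal because the two proportions are equal. A Wilcoxon test on worst grade has about 31% power (simulation, 3,000 runs), and a chi-square on G3 has 54%. Under these assumptions the difference is visible only above the G2 cut.

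**The case against.** The removal is disclosed under the SAP's heading for deviations. The endpoint is one of several secondaries that SAP 9.3 calls exploratory. SAP 6.2 places the final analysis after database lock. The stated reason is worded for patients as a whole, not by arm. All of this stands, and it limits the weight of the point.

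A reader might infer that the sponsor dropped the analysis after seeing an unfavourable comparison. The documents do not support that: they do not say whether grades were seen pooled or by arm, or when. They do not exclude it either, so the point is a risk. The SAP's tense is also uneven, since section 10 still writes of enrolment as future, although sections 2 and 7 describe it as complete.

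A reader might also infer that a planned G3 comparison was removed. It was not. The protocol planned an ANOVA on worst grade, which gives a difference in mean grade and does not isolate G3. A separate G3 contrast would be new.

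Low power could be offered as a reason to leave the analysis out. The SAP does not give that reason. The 9% figure rests on week-5 rates for an endpoint with a longer window, and a table of counts by arm needs no power. ANOVA is a weak method for a graded scale, but that argues for a supporting test, not for removal.

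**Conclusion.** The point holds, as something that should be fixed. A pre-specified secondary analysis was removed for a reason that is itself a trial outcome and does not make the endpoint uninformative. The SAP is left inconsistent: sections 3.2 and 5.2 list an endpoint that sections 11, 13 and 14 do not analyse. What is lost is the only planned efficacy comparison using grades above the G2 cut.

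The consequence is limited. The primary analysis, time to G2, Skindex-16, ITA and TEWL are unaffected, and selective reporting is not shown. Per cancer site, chi-square power for a G3 contrast runs from 9% at the documents' week-5 rates to 84% at an assumed 50% vs 10%. The range rests on 20 evaluable patients per arm, on assumed full-course rates, and on applying head and neck rates to breast.

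**What to change.** Delete the exclusion in SAP section 13 and restore worst CTCAE grade in sections 11.4.2, 11.5 and 14.2 as an exploratory secondary endpoint:

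- a table of worst grade by arm within each cancer site, counting patients withdrawn at G3 at the grade they reached;
- the pre-specified ANOVA;
- labelled as post hoc supporting analyses, a rank or ordinal test, and the proportions with G3 or higher with their difference and 95% CI.

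In section 13, state what outcome data, pooled or by arm, had been seen when the decision was made.

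The cost is one table and up to three short analyses per cancer site, plus one sentence. Protocol 6.4.2 has skin toxicity assessed at every visit, so no new data are needed.

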## 14. LIST AND SAMPLES OF TABLES, FIGURES AND GRAPHS

*Table 5.1.1.1. Subject disposition (Breast cancer)*

*Table 5.1.1.2. Dropout patients (Breast cancer)*

*Table 5.1.2.1. Subject disposition (Head and neck cancer)*

*Table 5.1.2.2. Dropout patients (Head and neck cancer)*

### 14.1 Demographic data

*Table 5.2.1.1. Demographic and baseline characteristics (Breast Cancer)*

*Table 5.2.1.2. Details about the disease at screening (Breast Cancer)*

*Table 5.2.2.1. Demographic and baseline characteristics (Head and Neck Cancer)*

*Table 5.2.2.2. Details about the disease at screening (Head and Neck Cancer)*

*Table 5.3.2.1. Compliance with device administration (Breast Cancer)*

*Table 5.3.2.2. Compliance with device administration (Head and neck cancer)*

### 14.2 Efficacy data

*Table 5.4.1.1.1. Number and proportion of subjects that reached and not reached G2 at week 5 (Breast cancer).*

*Table 5.4.1.2.1. Number and proportion of subjects that reached and not reached G2 at week 5 (Head and neck cancer).*

*Figure 5.4.2.1.1. Kaplan-Meier curves for time to G2 by treatment group (Breast cancer)*

*Table 5.4.2.1.1 Number and proportion of subjects that reached and not reached G2 at week 6 and 2 weeks after end of radiotherapy treatment (Breast cancer).*

*Table 5.4.2.1.2 Skindex-16 at Visits 7, 8, 9 and worst Skindex-16 observed in breast cancer patients*

*Table 5.4.2.1.3 Skindex-16 at Visits 7, 8, 9 and worst Skindex-16 Emotional observed in breast cancer patients*

*Table 5.4.2.1.4 Skindex-16 at Visits 7, 8, 9 and worst Skindex-16 Functional observed in breast cancer patients*

*Table 5.4.2.1.5. Changes in ITA among breast cancer patients*

*Figure 5.4.2.1.2 Mean ITA observed during the study (Breast cancer)*

*Table 5.4.2.1.6. Changes in TEWL among breast cancer patients*

*Figure 5.4.2.1.2. Mean TEWL observed during the study (Breast cancer)*

*Table 5.4.2.1.7. Patient's global satisfaction with treatment (Breast cancer)*

*Figure 5.4.2.2.1. Kaplan-Meier curves for time to G2 by treatment group (Head and neck cancer)*

*Table 5.4.2.2.1 Number and proportion of subjects that reached and not reached G2 at week 6 and 2 weeks after end of radiotherapy treatment (Head and neck cancer).*

*Table 5.4.2.2.2 Skindex-16 at Visits 7, 8, 9 and worst Skindex-16 observed in head and neck cancer patients*

*Table 5.4.2.2.3 Skindex-16 at Visits 7, 8, 9 and worst Skindex-16 Emotional observed in head and neck cancer patients*

*Table 5.4.2.2.4 Skindex-16 at Visits 7, 8, 9 and worst Skindex-16 Functional observed in head and neck cancer patients*

*Table 5.4.2.2.5. Changes in ITA among head and neck cancer patients*

*Figure 5.4.2.2.2 Mean ITA observed during the study (Head and neck cancer)*

*Table 5.4.2.2.6. Changes in TEWL among head and neck cancer patients*

*Figure 5.4.2.2.2. Mean TEWL observed during the study (Head and neck cancer)*

*Table 5.4.2.2.7. Patient's global satisfaction with treatment (Head and neck cancer)*

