Phase of the study	Screening	RT & treatment start	RT (expected 33-35 sessions)						RT end	2 weeks treatment without RT
Visit number	1	2	3	4	5	6	7	8	9	10
Week	-	0	1	2	3	4	5	6	7	9
Time (Days) ± 2 days	-3 to 0	1	7	14	21	28	35	42	49	63
Informed consent signature	X									
Inclusion/Exclusion criteria	X	X								
Patient randomization		X								
Socio-demographic data	X									
Medical and surgical history collection	X									
Physical examination	X	X	X	X	X	X	X	X	X	X
Concomitant medications and therapies	X	X	X	X	X	X	X	X	X	X
ECOG performance status	X									
Erythema assessment	X	X	X	X	X	X	X	X	X	X
Skindex-16 questionnaire	X	X	X	X	X	X	X	X	X	X
Spettrophotometry & TEWL		X	X	X	X	X	X	X	X	X
Study treatment dispensation to patient		X							X	
Study treatment return and accountability									X	X
Patient diary dispensation		X							X	
Patient diary collection									X	X
Patient Global Satisfaction score									X	X
Adverse events		X	X	X	X	X	X	X	X	X

Study Flow-Chart for breast cancer subjects

Phase of the study	Screening	RT & treatment start	RT (expected 30 sessions)						RT end	2 weeks treatment without RT
Visit number	1	2	3	4	5	6	7	8		9
Week	-	0	1	2	3	4	5	6		8
Time (Days) ± 2 days	-3 to 0	1	7	14	21	28	35	42		56
Informed consent signature	X									
Inclusion/Exclusion criteria	X	X								
Patient randomization		X								
Socio-demographic data	X									
Medical and surgical history collection	X									
Physical examination	X	X	X	X	X	X	X	X		X
Concomitant medications and therapies	X	X	X	X	X	X	X	X		X
ECOG performance status	X									
Erythema assessment	X	X	X	X	X	X	X	X		X
Skindex-16 questionnaire	X	X	X	X	X	X	X	X		X
S Spettrophotometry & TEWL		X	X	X	X	X	X	X		X
Study treatment dispensation to patient		X							X	
Study treatment return and accountability									X	X
Patient diary dispensation		X							X	
Patient diary collection									X	X
Patient Global Satisfaction score									X	X
Adverse events		X	X	X	X	X	X	X		X

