#### Skindex-16 questionnaire

The Skindex-16 scale is a self-administered questionnaire to comprehensively measure the complex effects of skin diseases on subject's quality of life. The Skindex-16 measure is considered appropriate for a study since it has been shown to be reliable and valid for general skin disease.

The Skindex-16 allows patient rating of emotional and functional burdens that the CTCAE does not take into account. These adverse events cause patient's discomfort and impact negatively on quality of life.

The Skindex-16 questionnaire will be completed by the subject at each visit.

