  model avg_TEWL = treatment avg_TEWL_baseline;
  run;
```

where avg\_TEWL and avg\_TEWL\_baseline have been obtained as follows:

```
TEWL_diff1 = tewl_rt1 - tewl_ct;
TEWL_diff2 = tewl_rt2 - tewl_ct;
```

```

TEWL_diff3 = tewl_rt3 - tewl_ct;
TEWL_diff4 = tewl_rt4 - tewl_ct;
TEWL_diff5 = tewl_rt5 - tewl_ct;
avg_TEWL #= mean(TEWL_diff1,TEWL_diff2,TEWL_diff3,TEWL_diff4,TEWL_diff5);

```

The mean and worst score of Skindex-16 questionnaire will be compared between treatment groups using ANCOVA, to adjust the estimates for baseline values.

The following SAS code will be used for ANCOVA analysis:

```

proc glm data = DB;
class treatment;
model skindex_score = treatment skindex_score_b1 ;
run;

```

Both the number of daily product applications reported on the patient's diary and the amount of used product, estimated through the difference in tubes weight between delivery to patient and return, will be used to assess the compliance to experimental treatment. The consistency between the two assessments will be checked through linear regression.

The patients' global satisfaction with treatment, assessed by Likert scale, will be compared between treatment groups using Kruskal-Wallis test.

```

proc npar1way;
class TREATMENT;
var satisfaction;
run;

```

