## 11.5 Summary of Efficacy Analyses

Endpoint	Analysis	Populations
Proportion of patients without G2 radiation dermatitis at week 5	The proportion of patients without G2 radiation dermatitis (radiation dermatitis < G2) at week 5 will be assessed and compared between treatment groups using chi-square test. Logistic regression will be performed to obtain Odds Ratio.	ITT
Median time to G2 radiation dermatitis development according to CTCAE	Median time to G2 radiation dermatitis will be analyzed using Kaplan-Meier method and compared between treatment groups using log-rank test.	ITT
Proportion of patients without G2 radiation dermatitis at week 6 for both cancer sites, at week 7 for head & neck cancer and 2 weeks after the last radiation for both cancer sites	The proportion of patients without G2 radiation dermatitis at week 6 for both cancer sites, at week 7 for head & neck cancer and 2 weeks after the last radiation for both cancer sites will be assessed and compared between treatment groups using chi-	ITT

weeks after the last radiation for both cancer sites.	square test. Logistic regression will be performed to obtain Odds Ratios	
Changes in skin erythema and pigmentation and trans-epidermal water loss (TEWL)	The changes in skin erythema and pigmentation and in trans-epidermal water loss (TEWL) will be graphically described throughout the study. Changes between before the first RT session and the end of RT and between the end of RT and the end of treatment will be analyzed and compared between treatment groups using ANCOVA, to adjust the estimates for baseline values.	ITT
Mean and worst score of Patient Reported Outcome (PRO) with Skindex-16 questionnaire performed weekly	Weekly mean and worst score of Skindex-16 questionnaire will be compared between treatment groups using ANCOVA, to adjust the estimates for baseline values.	ITT
Compliance to experimental treatment use	The compliance with the treatment will be assessed through a diary where the patient will record the daily product applications and through the difference in weight of tubes when delivered to patient and when returned by the patient. The consistency between the two assessments will be checked.	ITT
Patient global satisfaction with treatment as assessed by Likert scale	The patients' global satisfaction with treatment, assessed by Likert scale, will be compared between treatment groups using Kruskal-Wallis test.	ITT

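### The SAP's Skindex-16 output list (visits 7, 8, 9 and worst) does not deliver the planned mean of a weekly questionnaire, and the visit subset is neither declared nor justified

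*SAP*

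**What the plan says.** SAP 5.2 defines the endpoint as "Mean and worst score of Patient Reported Outcome (PRO) with Skindex-16 questionnaire performed weekly". The protocol synopsis and Protocol 5.2 agree in substance.

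Protocol 7.3.5.2 gives the analysis: "The mean and worst score of Skindex-16 questionnaire will be compared between treatment groups using ANCOVA, to adjust the estimates for baseline values". SAP 11.4.2 repeats this and supplies one generic model line, "model skindex_score = treatment skindex_score_b1", with no rule for forming the mean or choosing a visit. The SAP 11.5 summary table words it slightly differently: "Weekly mean and worst score of Skindex-16 questionnaire will be compared between treatment groups using ANCOVA, to adjust the estimates for baseline values".

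On collection, SAP 9.1 states: "The Skindex-16 questionnaire will be completed by the subject at each visit".

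SAP 14.2 lists six Skindex-16 tables, three per cancer site: one with no subscale named, one Emotional and one Functional. The first breast title is "Skindex-16 at Visits 7, 8, 9 and worst Skindex-16 observed in breast cancer patients". The other five use the same visit numbers plus the worst score.

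SAP 13 declares one departure from the protocol analysis, the dropping of worst skin toxicity. It says nothing about Skindex-16.

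**The concern.** The tables that the SAP lists do not contain one of the two summaries that the endpoint names. If the report follows the list, a reader will see three late visits and a worst score, and will not know which result answers the endpoint.

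The three visits appear nowhere in the protocol as a Skindex-16 selection, and no reason is given for them. SAP version 1.0 is dated 18 December 2018. Its sections 2 and 7 describe the patients as already enrolled, and section 13 cites an outcome, that most patients had reached G2. An unexplained subset of visits that first appears at that stage of an open-label trial carries a selective-reporting risk, even with no sign that results guided it.

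Comparisons at visits 7-9 also lose patients who left earlier. G3 toxicity ends participation (Protocol 6.1 and 16.1) and missing values are not replaced (SAP 9.1.4). The plan's background reports week-5 G3 of about 10% in the historical cohort and 2% in the pilot, so such losses could differ by arm.

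**Working it through.** The plan gives no numerical figure for this endpoint. Its only sample-size calculation concerns the primary endpoint and is not an input here.

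**Step 1: scheduled visits (Protocol Appendix 2 flow-charts).** Visits 1 and 2 precede the first radiotherapy session, so post-baseline visits start at visit 3.

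| | Post-baseline visits | Weeks | Listed in SAP 14.2 | Not listed |
|---|---|---|---|---|
| Breast | 3-9 (7 visits) | 1-6 and 8 | 7, 8, 9 = weeks 5, 6, 8 | 3-6 = weeks 1-4 |
| Head and neck | 3-10 (8 visits) | 1-7 and 9 | 7, 8, 9 = weeks 5, 6, 7 | 3-6 and 10 = weeks 1-4 and 9 |

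Unlisted share: breast 4/7 = 57%; head and neck 5/8 = 62.5%. Visit 9 is the final visit, two weeks after radiotherapy, in breast. In head and neck it is the end of radiotherapy. The same visit numbers therefore stand for different time points, and head and neck has no table for the final visit.

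**Step 2: test the list against each reading of the endpoint.**
- Reading A, one mean per patient over the weekly scores: no listed table carries it in either site.
- Reading B, the group mean at each week: weeks 1-4 are missing in both sites, and week 9 in head and neck.

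The list is incomplete under both, so the ambiguity does not resolve the conflict.

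**Step 3: what the choice of summary does to precision (assumption only).** The documents give no SD or between-visit correlation. Assume equal variances, a common correlation ρ and no baseline adjustment. For k visits,

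SE(mean of k visits) / SE(one visit) = √[(1 + (k − 1)ρ)/k].

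For k = 7 (breast):
- ρ = 0.4: √(3.4/7) = 0.70
- ρ = 0.6: √(4.6/7) = 0.81
- ρ = 0.8: √(5.8/7) = 0.91

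This is precision, not power. If the effect were equal at visits 7-9 and zero before, the averaged effect would be 3/7 = 0.43 of the single-visit effect. Its signal-to-SE ratio relative to one late visit would then be:
- ρ = 0.4: 0.429/0.697 = 0.61
- ρ = 0.6: 0.429/0.811 = 0.53
- ρ = 0.8: 0.429/0.910 = 0.47

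The mean is the better summary if the effect is spread over the weeks and the worse one if it is only late. The two answer different questions, so the plan has to say which one is the endpoint.

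**The case against.** SAP 14.2 is a list of table titles, and nothing says that it overrides section 11. It is loose elsewhere too: in each site one figure number is used twice, an adverse-event table title is repeated, and head and neck has no week 7 table for the G2 proportion although 11.4.2 plans that comparison. The secondary endpoints are declared exploratory, without multiplicity correction (Protocol 7.3.2, SAP 9.3). All of this stands, and it limits the point to an internal conflict on an exploratory endpoint.

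Four stronger readings are tempting and are not supported.

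- *The mean has been replaced and will never be produced.* SAP 11.4.2 and 11.5 still plan it.
- *The week 1-4 questionnaires are discarded.* They can enter the worst score, which is tabulated, and may appear in listing VI.6 of individual efficacy data.
- *The endpoint is unambiguously the per-patient mean of the weekly scores.* The wording also fits a mean at each week. The single-response model does not settle it, because 11.4.2 uses the same form of model for ITA with averages formed at each timepoint.
- *Three visit tests inflate the false-positive rate over one planned test.* That needs an assumed correlation and takes reading A for granted. Under reading B, seven tests per breast scale were already planned, so three is fewer. The worst score is a further planned comparison under either reading.

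The documents also do not show that outcome data drove the choice of visits 7-9.

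**Conclusion.** The conflict is real. SAP 14.2 does not match SAP 5.2, 11.4.2 and 11.5 or Protocol 7.3.5.2. No listed table gives a mean over the weekly scores, and by-visit results are unlisted for 4 of 7 post-baseline visits in breast and 5 of 8 in head and neck. These counts rest only on the Appendix 2 schedule and the table titles. The precision figures rest on assumed correlations and serve only to show that the choice of summary matters.

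The subset is undeclared in SAP 13 and was set down after enrolment. It should be corrected because producing the outputs as listed would report unexplained late visits where the pre-specified mean belongs. The primary conclusion is not affected.

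**What to change.** 1. In SAP 11.4.2, define the Skindex-16 mean as each patient's mean over all available post-baseline visits (breast 3-9, head and neck 3-10), and analyse it with the baseline-adjusted ANCOVA already planned. State how missed visits and withdrawals are handled, including whether an end-of-study questionnaire completed at discontinuation (Protocol 16.1) counts.
2. In SAP 14.2, add a table for this mean in each cancer site and keep the worst score. Show by-visit results for all post-baseline visits, including head and neck visit 10, as descriptive detail.
3. If the visit 7-9 subset is kept, declare and justify it in SAP 13 as a change from the protocol.

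A repeated-measures model over the same visits, reporting the visit-averaged treatment difference, is an acceptable alternative if declared in SAP 13. It uses the partial data of patients who leave early. Neither approach by itself resolves withdrawal at G3, which is related to outcome: a patient who leaves early contributes only early weeks. Reporting the number of visits contributed, by arm, would let readers judge this.

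The cost is SAP wording, one derived variable per scale and a few tables, with no new data. The downside is that averaging in mild early weeks can dilute an effect that appears only late. The by-visit display would still show it.
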